5.1.8 World Health Organization Drinking Risk Categorical Scale

The WHO has developed a drinking risk categorical scale that can be used in a responder analysis approach to assess clinically relevant decreases in alcohol consumption (Aubin et al., 2015). Two dichotomous endpoints will be analyzed: WHO 1-level and WHO 2-level decrease in alcohol consumption. The WHO 1-level and 2-level decrease endpoints are the percentage of subjects experiencing at least a 1-level or 2-level decrease in WHO levels of alcohol consumption, respectively, from the level at baseline (the period including the 28 days before screening) to the level during period of interest. The WHO levels of average alcohol consumption per day are as follows:

	Males	Females
Low Risk	1 to 40g	1 to 20g
Medium Risk	41 to 60g	21 to 40g
High Risk	61 to 100g	41 to 60g
Very High Risk	101+g	61+g

where 14g = 1 SDU (WHO2000). In computing the alcohol consumption level, average drinks per day will be used, computed as the sum of all drinking in the 28 day period divided by the number of days with non-missing drinking data in that period. Abstinent subjects will be included in a separate "Abstinent" category. A subject must have at least 1 week of data during a month to be considered non-missing.

5.2 Alcohol Use Disorder (MINI Version 7 – DSM5)

The AUD module of the MINI Neuropsychiatric Interview (MINI) specifies the severity of AUD into 3 categories based on the total number of symptoms to which the subject is coded "Yes" as follows:

Mild = 2 to 3 symptoms

Moderate = 4 to 5 symptoms

Severe = 6 or more symptoms

Subjects must have at least 4 symptoms to be eligible to participate in the study. The total number of symptoms being scored is 11. No imputation for missing values will be used.

5.3 Barrett Impulsiveness Scale

The Barratt Impulsiveness Scale (BIS) is a questionnaire designed to assess the personality/behavioral construct of impulsiveness. It is a 30-item scale with items scored on a 4-point scale (1=rarely/never; 2= occasionally; 3=often; 4=almost always/always). Items 1, 7, 8, 9, 10, 12, 13, 15, 20, 29, and 30 are reverse scored. The total score is the sum of the individual items. Separate subscale scores for Self-Control and Impulsive behavior will also be calculated. The BIS is among the baseline assessments that are performed only at Week 1.

5.4 Smoking and Cigarettes Smoked per Week

A quantity frequency interview at baseline and during treatment will include two questions to assess cigarette smoking behavior: 1) Over the past week, on how many days did you smoke cigarettes?; and 2) On the days you smoked during the past week, how many cigarettes did you smoke on average? At baseline subjects that answer "0" to question #1 are considered non-smokers for the study. Cigarettes per week is the answer to question #2 multiplied by the answer to question #1. No imputation for missing values will be used.

5.5 Nicotine use and Days of Other Nicotine Use per Week

The cigarette smoking questionnaire will include a third question: 3) Over the past week, on how many days did you use other nicotine products (ex. chew, cigars, cigarillos, e-cigarettes, vape, gum, patch, etc...). A subject is positive for any nicotine use if the number of smoking days or the number of any other nicotine use days is greater than zero.

5.6 Experiences in Close Relationships – Relationship Structures Questionnaire (ECR-RS)

The Experiences in Close Relationships-Relationship Structures scale (Farley et al, 2011) is a questionnaire assessing two-dimensional relationship-specific attachment structures in adults beyond the traditional focus on romantic relationships. This is a 36-item questionnaire, of which only the first 18-item attachment-related anxiety scale will be assessed and evaluated. The presentation of the items were randomized on the form for subject completion. Each item is rated on a 7-point scale where 1 = strongly disagree and 7 = strongly agree. The attachment-related anxiety is determined by averaging the scores of these 18 items. However, items 9 and 11 are "reverse keyed".

5.7 Hyperkatifeia

Hyperkatifeia is defined as a greater intensity of negative emotional/motivational signs and symptoms during withdrawal from drugs of abuse in the withdrawal/negative affect stage of the addiction cycle (Koob 2021). Hyperkatifeia or negative emotional state is considered to be one of stages of addiction in the context of drug withdrawal (Koob and Le Moal 1997, Koob 2019). NIAAA has developed a 24-item self-report Hyperkatifeia Scale to capture negative emotionality after stopping alcohol drinking that will be assessed for the first time in this study of heavy drinkers with a diagnosis of moderate to severe AUD. The items address four measures associated with negative emotional state including anxiety, depression, stress, irritability and pain. Each item is is 5-point Likert scale assessing the intensity of the feelings and sensations experienced when not drinking alcohol. Higher scores are indicative of greater intensity of hyperkatifeia.

5.8 Inventory of Drinking Situations (IDS-30)

The IDS-30 is a 30-item patient completed questionnaire of reward and relief drinking that asks subjects to rate the frequency (0= never, 3 = almost always) of heavy drinking in various situations over the past year (Mann et al, 2018). Fifteen items measure reward drinking

tendencies and 15 items measure relief drinking tendencies. A subsequent evaluation of IDS-30 refined the definition of reward drinking to five items and relief drinking to five items (Votaw et al, 2022)

The reward drinking score is determined by summing the scores for these items: 6, 18, 21, 23, 27.

The relief drinking score is determined by summing the scores for these items: 9, 14, 15, 22, 25

Missing data is not imputed. All five questions within each scale must be answered for a score to be computed; otherwise, the scale is missing.

5.9 PROMIS Questionnaires

PROMIS® (Patient-Reported Outcomes Measurement Information System) is a set of personcentered measures that evaluates and monitors physical, mental, and social health in adults and children that were developed through the support of U. S. Department of Health and Human Services (https://www.healthmeasures.net/explore-measurement-systems/promis). Three of these assessments, described below, will be utilized in this study.

5.9.1 PROMIS – Alcohol-related Negative Consequences

For negative consequences for alcohol use, the PROMIS Alcohol Negative Consequences – Short Form 7a questionnaire will be used to assess outcomes of alcohol use over the past 30 days. Each of the 7-items assesses the frequency of the negative alcohol-related consequence on 5-point Likert scale with higher scores indicating greater frequency. The scoring manual will be used to compute T-scores for each evaluation. All 7 questions must be answered for the form to be considered non-missing.

5.9.2 PROMIS – Sleep Disturbances

For assessment of subject's sleep quality, the PROMIS Sleep Disturbance – Short Form 8b will be used. The questionnaire consists of 8 questions regarding the quality of sleep over the past 7 days. Each item on the measure is rated on a 5-point scale with a range of scores from 8 to 40 with higher scores indicating greater severity of sleep disturbance. The American Psychiatric Association has established levels of severity (none to slight [<55], mild [55.0 - 59.9], moderate [60 - 69.9] or severe [70 or higher] based on the T-score derived from a conversion table) {add reference to APA website|. At least 5 questions must be answered to be considered non-missing.

5.9.3 PROMIS – Pain Interference

For the assessment of pain interference, the shortened 8a version of the PROMIS for pain interference will be used to measure the self-reported consequences of pain over the past 7 days. This 8-item questionnaire assesses the degree to which pain interferes with various activities. Each item on the measure is rated on a 5-point scale with higher scores indicating greater pain

interference. The scale ranges from 8 to 40. The scoring manual will be used to compute T-scores for each evaluation. At least 5 questions must be answered to be considered non-missing.

5.10 Profile of Mood States (POMS)

The POMS measures dimensions of affect or mood (McNair and Heuchert 2005). It consists of 65 adjectives to which the subject responds according to a 5-point scale ranging from "not at all (0)" to "extremely (5)." Six subscale scores will be computed for items grouped as follows: Tension-Anxiety, Depression-Dejection, Anger-Hostility, Vigor-Activity, Fatigue-Inertia, and Confusion-Bewilderment. A Total Mood Disturbance score will also be computed which consists of the sum of Tension-Anxiety, Depression-Dejection, Anger-Hostility, Fatigue-Inertia, and Confusion-Bewilderment scores then subtracting the Vigor-Activity subscale score. A missing value within a subscale will be replaced by the average score of the answered items within the subscale; if 2 or more items within a subscale are missing then the entire subscale will be considered missing.

5.11 Urge to Drink Scale (UDS)

The UDS is a modified version of an assessment that was developed and validated by researchers at the University of Pennsylvania's Center for Studies of Addiction. This measure has been shown to be a valid and reliable instrument for assessing an individual's urge to drink alcohol. This scale has 5 items with 7 different responses to each item scored as 0 to 7. The questions pertain to the past week. The total score is the sum of the point scores for the individual items. Total scores of 10 or higher during treatment have been reported to be associated with increased risk for relapse. Missing values will not be imputed.

6.0 HYPOTHESES TO BE TESTED

6.1 Primary Efficacy Endpoint

It is hypothesized that oxytocin, as compared to placebo will reduce the weekly percentage of heavy drinking days over the 10-week maintenance period (study weeks 3-12). This hypothesis will be tested using other time periods during treatment.

6.2 Secondary Efficacy Endpoints

Over the 10-week maintenance period (study weeks 3-12), it is hypothesized that the oxytocin group, as compared to the placebo group, will:

- 1. Increase the percentage of subjects with no heavy drinking days
- 2. Increase the percentage of subjects abstinent from alcohol
- 3. Increase the percentage of subjects with a WHO drinking risk category decrease of:
 - a. 1-level
 - b. 2-levels
- 4. Increase the percentage of days abstinent per week

- 5. Decease the weekly mean number of drinks per week
- 6. Decrease the weekly mean drinks per drinking day
- 7. Decrease the number of MINI AUD symptoms
- 8. Decrease the cigarettes smoked per week among smokers
- 9. Increase the smoking abstinence rate among smokers
- 10. Decrease the weekly number of days of other nicotine use among other nicotine users
- 11. Increase the nicotine use abstinence rate among nicotine users (includes cigarettes)
- 12. Decrease in attachment related anxiety scores of the ECR-RS (attachment related anxiety)
- 13. Decrease in PROMIS sleep disturbance, alcohol-related negative consequences, and pain interference scores
- 14. Decrease in POMS subscales total mood disturbance, anger-hostility, fatigue-inertia, confusion-bewilderment, tension-anxiety and depression scores and/or increase vigor-activity
- 15. Decrease in the Urge to Drink scale scores

7.0 SAMPLE SIZE CONSIDERATIONS

With an intake sample of 100 subjects (50 subjects per arm) and 12% attrition, it is projected that the sample size for primary endpoint analyses will be 88 (44 subjects per arm). The alpha level for the primary analyses will be 0.05, two-tailed. An estimate of the effect size (Cohen's d) for the investigational products is 0.60. Equal variances in both groups are assumed. These assumptions lead to a projected power of 0.80.

8.0 DATA QUALITY ASSURANCE

Data quality assurance will start with training of clinical investigative staff on data collection and assessment procedures including a Manual of Operations that describes what data to collect and procedures for completion of electronic case report form (eCRFs.) Completed eCRFs will be reviewed by Fast-Track Drugs and Biologics clinical monitors on a regular basis throughout the trial by comparison against the source documents.

All study data will come from the eCRFs and no other source data. eCRFs for this study were created using an electronic data management system (EDMS) based on Merge eClinicalOS. eCRFs were created using an established data dictionary for each variable including the field name, field type, field attributes, and coding for variables. Range checks, alpha-numeric requirements, and null/not null parameters were programmed as applicable. The back end database application is Oracle. Data entered into the EDMS system will be reviewed by Fast-Track clinical monitors and data managers. If incomplete or inaccurate data are found, the data will be queried in the system for site staff to address. The site will resolve data inconsistencies and errors using the EDMS with full audit trail of corrections being maintained within the

system. Corrections and changes to the data will be reviewed by Fast-Track clinical monitors and data managers.

Additional edit checks will be written to detect anomalies in the database. These checks will address inconsistencies (within visits, across visits), invalid/unusual values, missing values, and protocol violations. Edit checking will be validated on test data or actual clinical trial data. In addition to programmed edit checks, quality control examination of data will also be performed on reviews of data listings.

9.0 STATISTICAL CONSIDERATIONS

9.1 General Considerations

For descriptive purposes, dichotomous and categorical variables will be presented as number of observations and percentages; continuous variables will be given as means, standard deviations (SD), median, minimum (min) and maximum (max). Statistical tests will be two-tailed at a 0.05 Type I error rate. P-values for the primary and secondary endpoints of < 0.05 will be considered statistically significant. Endpoint data will also be screened for outliers and skewness. Appropriate non-parametric tests will be used to compare treatment groups on continuous baseline characteristics that are not normally distributed. Continuous endpoint data that are not normally distributed will be transformed using either a square root, logarithmic, or inverse transformation, the selection of which is determined by skewness and kurtosis statistics with values closest to zero and normalization of histograms. Cohen's d will be used to calculate the effect size for means. Odds ratios will be provided for all dichotomous outcomes. Descriptive statistics – mean, SD, median, min and max – of all endpoint data will be provided for each assessment point or summarized at each week for drinking endpoints. All data will be presented in listings. All analyses will be performed in the full analysis set.

9.2 Participant Accountability and Protocol Deviations

A summary will be prepared to show dropouts/retention over time in each group, along with the reason for early termination. The number of missing observations will be presented between groups. Protocol deviations will be presented as summaries by type of deviation.

9.3 Demographics and Other Baseline Characteristics

Summaries of the characteristics of the subjects in each of the study groups at baseline will be prepared for the full analysis set. Demographic characteristics (e.g., age, gender, race, and ethnicity) and other baseline characteristics including Barratt Impulsiveness scale (BIS), mood scales (e.g., Spielberger Trait Anxiety Inventory (STAI), Buss-Perry Aggression Questionnaire (BPAQ), POMS total and subscale scores), hyperkatifeia questionnaire, ECR-RS, Simplified Nutritional Appetite Questionnaire (SNAQ), PROMIS scales for alcohol negative consequences, sleep disturbances, and pain interference, University of Pennsylvania Smell Identification Test (UPSIT), and drinking goal) will be summarized by treatment group.

Baseline drinking parameters in the 28-days prior to the start of screening, age started drinking regularly, medical treatments for drinking in the past year, and other services used for alcohol problems in the past 4 weeks prior to consent will be summarized by treatment group. The

number and percentage of subjects with mild, moderate and severe symptoms of AUD and summary statistics for total number of symptoms will also be presented.

The numbers and percentages of subjects who are smokers, used any nictonine, used any other nicotine products, and any THC will be presented. The quantity of cigarettes smoked per week will be presented among smokers, and the number of days of other nicotine products used per week will be presented among subjects with any other nicotine product use.

Baseline drinking-associated consequences (CIWA-AR), alcohol craving (Urge to Drink Scale) total score, and Inventory of Drinking Situations (IDS) subscales of reward drinking and relief drinking will be summarized in a table.

Continuous variables will be summarized using means, standard deviations, medians, min, and max values. Categorical variables will be summarized using counts and percentages.

The comparability among the treatment groups with respect to the demographic and baseline variables will be evaluated by appropriate statistical methods. These will include t-tests for continuous variables, chi-square tests for categorical variables, and Fisher's exact test for binary variables. If a continuous variable is skewed, then the Wilcoxon rank sum test will be used on the raw data or a t-test on an appropriately transformed variable.

9.4 Efficacy Analysis

9.4.1 Primary Analysis of Primary Efficacy Endpoint

The primary efficacy endpoint is the weekly percentage of heavy drinking days during the 10-week maintenance period (study weeks 3-12). The primary analysis of the primary endpoint will be a fully covaried, mixed-effect model for repeated measures employed on the Full Analysis Set (using an appropriate transformation of the endpoint, if needed; see Section 9.1). Treatment group, study week, treatment group by study week interaction, clinical site and baseline percentage of heavy drinking days will be covariates in the mixed effects model. The analyses will be performed using SAS PROC MIXED procedure Subjects are treated as a class variable and not continuous. The week, treatment group, and clinical site are also treated as class variables. Additional covariates may be selected using the method described in Section 9.4.3. The solution statement from SAS PROC MIXED is requested to provide the solution for the fixed effects parameters. A REPEATED statement specifies that values are repeated each week and subjects are nested within treatment group. The covariance structure is specified.

The selection of the covariance structure is performed using a simple repeated mixed effects model that includes treatment group as the only fixed effect and subject nested within treatment group as the only random effect. The covariance structure is selected from autoregressive, compound symmetry, Toeplitz, and unstructured. The Akaike Information Criterion (AICc) corrected for a finite sample is obtained from each of the four models for the four possible covariance structures to determine model fit. The smallest (minimum) AICc associated with one of the covariance structures is selected and the difference for each of the other three covariance structures is calculated. A graph is produced of the model fit statistics and relative difference for the four possible covariance structures.

If the primary endpoint requires a transformation, another mixed effect model that is identical to the primary analysis model will be run using the untransformed endpoint. Results based on the primary analysis model and the model of the untransformed endpoint will be presented in tabular form. The overall least squares means and least square means for each time point along with the 95% confidence intervals (CI) will be presented for the untransformed endpoint only (for descriptive purposes), while two-tailed p-values and Cohen's d will be presented for both the untransformed and transformed data. Inference and Cohen's d will be based upon the results using appropriately transformed data. A graph of the primary endpoint will be produced using the LSMEANs from the untransformed endpoint with p-values and Cohen's d comparing weekly differences obtained from the appropriately transformed variable.

Descriptive statistics will be reported for all study weeks (1-12) by treatment group.

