# 7.3. Selection and Withdrawal of Subjects

### 7.3.1. Inclusion Criteria

Subjects must meet each one of the following inclusion criteria in order to be eligible for participation in the study:

- 1. Be at least 21 years of age.
- 2. Have a current (past 12 months) DSM-5 diagnosis of AUD (4 or more symptoms) assessed using the MINI neuropsychiatric interview version 7.0.2 (at least moderate severity, ICD-10-CM Code F10.20 alcohol dependence, uncomplicated).
- 3. If male, report drinking an average of at least 28 drinks per week or if female report drinking an average of at least 21 drinks per week and at least one heavy drinking day per week for the 28-day period prior to consent and at least one heavy drinking day in the 7- day period prior to randomization.

Version 4.0 (5Jul2022) 36 NIAAA Confidential

- 4. Have a BAC by breathalyzer equal to 0.000 when s/he signed the informed consent document (either just prior to or immediately after signing consent).
- 5. Be seeking treatment for problems with alcohol and express a goal of abstinence or a reduction in drinking.
- 6. Be able to verbalize an understanding of the consent form, able to provide written informed consent, verbalize willingness to complete study procedures, able to understand written and oral instructions in English and able to complete the questionnaires required by the protocol.
- 7. Agree (if the subject is female and of childbearing potential) to use at least one of the following methods of birth control, unless she is surgically sterile, partner is surgically sterile or she is postmenopausal:
  - oral contraceptives,
  - contraceptive sponge,
  - patch.
  - double barrier (diaphragm/spermicidal or condom/spermicidal),
  - intrauterine contraceptive system,
  - etonogestrel implant,
  - medroxyprogesterone acetate contraceptive injection,
  - complete abstinence from sexual intercourse, and/or
  - hormonal vaginal contraceptive ring.
- 8. Be able to take intranasal investigational products and be willing to adhere to the investigational product regimen.
- 9. Complete all assessments required at screening and baseline.
- 10. Have a place to live in the 2 weeks prior to randomization and not be at risk that s/he will lose his/her housing by Study Week 15.
- 11. Not anticipate any significant problems with transportation arrangements or available time to travel to the study site by Study Week 15.

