## 7.5. Baseline and Final Eligibility Assessments

If the subject is eligible after performing all the initial screening assessments, s/he will be scheduled to start the study and will come to the clinic for a final eligibility check including the following assessments:

- Alcohol breathalyzer
- Urine drug screen
- Update medical history
- Update physical exam new symptoms directed exam
- Vital signs
- CIWA-AR
- C-SSRS\*
- Pregnancy test for females of childbearing potential (must be completed within 2 days prior to the subject being randomized and dispensed investigational product)
- Birth control methods, if female
- Prior medications update
- TLFB since screening visit

\*Note that the MINI will be used to rule out subjects who attempted suicide in the past year and current (past year) suicidal ideation at initial screening, with the C-SSRS providing an update on current suicidal ideation since screening.

An eligibility checklist will be completed and reviewed by a study investigator and, if the subject is still eligible, he/she will complete the following baseline assessments:

• Other Services for Alcohol Use Problems

The subject will complete the following questionnaires electronically:

- Hyperkatifeia Scale
- Barrett Impulsivity Scale
- Cigarette Smoking Quantity-Frequency and Other Nicotine Use
- Buss-Perry Aggression Questionnaire Short Form
- Experiences in Close Relationships-Relationship Structures
- PROMIS Alcohol Negative Consequences
- PROMIS Sleep Disturbances
- PROMIS Pain Interference
- POMS
- IDS-30
- Spielberger Trait Anxiety Scale
- Urge to Drink Questionnaire
- SNAQ

The screening period will not be extended. If the investigator determines that the subject could be a viable participant who could not for extenuating circumstances complete the screening period in 14-days, the subject can be re-screened by completing all of the screening assessments again. In this case, the subject will be assigned a new subject number.

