Number Lifetime Hospitalizations to Reduce/Quit Drinking	xx	XX	xx	0.xxx
Mean (SD)	xx.x (xx.xx)	xx.x (xx.xx)	xx.x (xx.xx)	U.XXX
Median Median	XX XX	XX	XX	
Min-Max	(xx-xx)	(xx-xx)	(xx-xx)	
Number Lifetime Hospitalizations for Illness/	(лл-лл)	(лл-лл)	(\(\lambda - \lambda \lambda\)	
Injuries due to Drinking N	VV	V.V	N.V.	0.xxx
Mean (SD)	XX XX.X (XX.XX)	XX XX.X (XX.XX)	XX XX.X (XX.XX)	U.XXX
Median (SD)	` ′	XX (XX.XX)	XX (XX.XX)	
Min-Max	(xx-xx)	(xx-xx)	(xx-xx)	
Number Outpatient Visits to Reduce/Quit	(۸۸-۸۸)	(AA-AA)	(۸۸-۸۸)	
Drinking in Last 12 Months				
N	XX	XX	XX	0.xxx
Mean (SD)	xx.x (xx.xx)	xx.x (xx.xx)	xx.x (xx.xx)	J.11111
Median	XX	XX	XX	
Min-Max	(xx-xx)	(xx-xx)	(xx-xx)	
Number Lifetime Medical Detoxifications	()	(1)	(-1111)	
N	XX	XX	XX	0.xxx
Mean (SD)	xx.x (xx.xx)	xx.x (xx.xx)	xx.x (xx.xx)	

	Placebo	Oxytocin	Total	
Characteristic	(N=xx)	(N=xx)	(N=xxx)	p-value ¹
Median	XX	XX	XX	
Min-Max	(xx-xx)	(xx-xx)	(xx-xx)	
Past Year Number of Support Group Meetings ⁴				
N	XX	XX	XX	0.xxx
Mean (SD)	xx.x (xx.xx)	xx.x (xx.xx)	xx.x (xx.xx)	
Median	XX	XX	XX	
Min-Max	(xx-xx)	(xx-xx)	(xx-xx)	

Note: Percentages are based on the number of non-missing values in each variable.

Table 14: Baseline Drinking by TLFB

	Placebo	Oxytocin	Total	
Parameter	(N=xx)	(N=xx)	(N=xxx)	p-value ¹
Percentage of Heavy Drinking Days (Pre-screening Days -1 to -28)				0.xxx
Mean (SD)	xx.x (xx.xx)	xx.x (xx.xx_	xx.x (xx.xx)	
Median	XX.X	XX.X	XX.X	
(Min – Max)	(xx.x - xx.x)	(xx.x - xx.x)	(xx.x - xx.x)	
Percentage of Heavy Drinking Days (7 Days Prior to Randomization)				0.xxx
Mean (SD)	xx.x (xx.xx)	xx.x (xx.xx_	xx.x (xx.xx)	
Median	XX.X	XX.X	XX.X	
(Min – Max)	(xx.x - xx.x)	(xx.x - xx.x)	(xx.x - xx.x)	
Percentage of Heavy Drinking Days (Percent Change Pre-screening Days -1 to -28 to 7 Days Prior to Randomization)				0.xxx
Mean (SD)	xx.x (xx.xx)	xx.x (xx.xx_	xx.x (xx.xx)	
Median	XX.X	XX.X	XX.X	
(Min – Max)	(xx.x - xx.x)	(xx.x - xx.x)	(xx.x - xx.x)	

¹p-value from t-test for continuous variables (t) – skewed continuous data uses the Wilcoxon rank-sum test (w) - chi-square test for categorical variables (c) – Fisher's exact test for dichotomous variables (f)

² No HDD and <=14 drinks per week for men or <=7 drinks per week women

³ Calculated using the subject's drinks per week during 28-day pre-screen period and the drinks per week obtained from the 7-day period on the Drinking Goal assessment

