⁴ Examples include Alcoholics Anonymous (AA), 12 step, Save Ourselves, or similar group meetings attended for alcohol problems or drinking

	Placebo	Oxytocin	Total	
Parameter	(N=xx)	(N=xx)	(N=xxx)	p-value ¹
Drinks/Week (Pre-screening Days -1 to -28)				0.xxx
Mean (SD)	xx.x (xx.xx)	xx.x (xx.xx_	xx.x (xx.xx)	
Median	XX.X	XX.X	XX.X	
(Min – Max)	(xx.x - xx.x)	(xx.x - xx.x)	(xx.x - xx.x)	
Drinks/Week (7 Days Prior to Randomization)				0.xxx
Mean (SD)	xx.x (xx.xx)	xx.x (xx.xx	xx.x (xx.xx)	
Median	XX.X	XX.X	XX.X	
(Min – Max)	(xx.x - xx.x)	(xx.x - xx.x)	(xx.x - xx.x)	
Drinks/Week (Percent Change Pre-screening Days -1 to -28 to 7 Days Prior to Randomization)				0.xxx
Mean (SD)	xx.x (xx.xx)	xx.x (xx.xx	xx.x (xx.xx)	
Median	XX.X	XX.X	XX.X	
(Min – Max)	(xx.x - xx.x)	(xx.x - xx.x)	(xx.x - xx.x)	
Drinks/Drinking Day (Pre-screening Days -1 to -28)				0.xxx
Mean (SD)	xx.x (xx.xx)	xx.x (xx.xx	xx.x (xx.xx)	
Median	XX.X	XX.X	XX.X	
(Min – Max)	(xx.x - xx.x)	(xx.x - xx.x)	(xx.x - xx.x)	
Drinks/Drinking Day (7Days Prior to Randomization)				0.xxx
Mean (SD)	xx.x (xx.xx)	xx.x (xx.xx	xx.x (xx.xx)	
Median	XX.X	XX.X	XX.X	
(Min – Max)	(xx.x - xx.x)	(xx.x - xx.x)	(xx.x - xx.x)	
Drinks/Drinking Day (Percent Change Pre-screening Days -1 to -28 to 7 Days Prior to Randomization)				0.xxx
Mean (SD)	xx.x (xx.xx)	xx.x (xx.xx_	xx.x (xx.xx)	
Median	XX.X	XX.X	XX.X	
(Min – Max)	(xx.x - xx.x)	(xx.x - xx.x)	(xx.x - xx.x)	
Percentage Days Abstinent (Pre-screening Days -1 to -28)				0.xxx
Mean (SD)	xx.x (xx.xx)	xx.x (xx.xx_	xx.x (xx.xx)	
Median	XX.X	XX.X	XX.X	
(Min – Max)	(xx.x - xx.x)	(xx.x - xx.x)	(xx.x - xx.x)	

	Placebo	Oxytocin	Total	
Parameter	(N=xx)	(N=xx)	(N=xxx)	p-value ¹
Percentage Days Abstinent (7 Days Prior to Randomization)				0.xxx
Mean (SD)	xx.x (xx.xx)	xx.x (xx.xx_	xx.x (xx.xx)	
Median	XX.X	XX.X	XX.X	
(Min – Max)	(xx.x - xx.x)	(xx.x - xx.x)	(xx.x - xx.x)	
Percentage Days Abstinent (Percent Change Pre-screening Days -1 to - 28 to 7 Days Prior to Randomization)				0.xxx
Mean (SD)	xx.x (xx.xx)	xx.x (xx.xx	xx.x (xx.xx)	
Median	XX.X	XX.X	XX.X	
(Min – Max)	(xx.x - xx.x)	(xx.x - xx.x)	(xx.x - xx.x)	
WHO Risk Level				0.xxx
High Risk	xx (xx.x%)	xx (xx.x%)	xx (xx.x%)	
Very High Risk	xx (xx.x%)	xx (xx.x%)	xx (xx.x%)	

Baseline Other Substance Use Table 15:

	Placebo	Oxytocin	Total	
Parameter	(N=xx)	(N=xx)	(N=xxx)	p-value ¹
Cigarette Smoker?				0.xxx
Yes	xx (xx.x%)	xx (xx.x%)	xx (xx.x%)	
No	xx (xx.x%)	xx (xx.x%)	xx (xx.x%)	
Any Nicotine Use?				0.xxx
Yes	xx (xx.x%)	xx (xx.x%)	xx (xx.x%)	

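### The primary model fixes one drinking covariate with no stated window; last-week drinking before randomization, already collected and tabulated, is left to an optional selection step

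*SAP*

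**What the plan says.** **The model.** SAP 9.4.1 specifies a repeated-measures mixed model for weekly PHDD in Weeks 3-12. Besides treatment, week and their interaction, "clinical site and baseline percentage of heavy drinking days will be covariates in the mixed effects model". No window is attached to baseline there, nor in the Baseline row of Table 23.

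**The window.** SAP 9.3 describes "Baseline drinking parameters in the 28-days prior to the start of screening". SAP 5.1.8 uses the same 28 days for the WHO risk level, and Listing 7 reports PHDD for Days -1 to -28.

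**What else is collected.** Screening may take up to 14 days. Protocol 7.5 lists "TLFB since screening visit" among the final eligibility assessments. Inclusion criterion 3 (Protocol 7.3.1) sets its drinking thresholds "for the 28-day period prior to consent and at least one heavy drinking day" in the 7 days before randomization.

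**What is tabulated.** SAP Table 14 has a row beginning "Percentage of Heavy Drinking Days (7 Days Prior to Randomization", and another for the percent change from the 28-day window to those 7 days, each by arm with a p-value. The same layout is used for days abstinent, in the row beginning "Percentage Days Abstinent (7 Days Prior to Randomization" and the percent-change row after it.

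**The optional route.** SAP 9.4.1 allows further covariates through 9.4.3. That section gives an open list (drinking goal, age and years of regular drinking are the examples) and asks for a correlation of at least 0.20 plus clinical expertise, judged on pooled blinded data. It specifies the correlation matrices against the secondary efficacy endpoints.

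**The concern.** Subjects are seeking treatment and have a goal of abstinence or reduction, so some may cut down between screening and the first dose. The entry rule allows this. One heavy day in the last 7 is enough, so PHDD in that week can be anywhere from 1/7 = 14% to 100%, even for a subject who was at 100% over the 28 days.

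The drinking level closest to the start of treatment is a plausible predictor of drinking in Weeks 3-12. If the model holds only the 28-day value, change before treatment stays in the residual, and any chance difference between arms in that change stays in the estimate. Table 14 is built to reveal such a difference, but nothing in the plan says what follows if it does. A covariate chosen after seeing that table by arm would be open to challenge.

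Table 14 also has a defect of its own. Percent change in percentage days abstinent divides by the 28-day value, so it is undefined for any subject with no abstinent day in that window. Percent change in PHDD does not have this problem, because entry requires a heavy day in each of the 28-day window's weeks.

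**Working it through.** **1. The plan's own power figure.** Inputs from SAP 7.0: 44 analyzed per arm (100 × 0.88 = 88), equal variances, "The alpha level for the primary analyses will be 0.05, two-tailed", and "An estimate of the effect size (Cohen's d) for the investigational products is 0.60". Normal approximation:

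power = Φ(d·√(n/2) − 1.96) = Φ(0.60 × √22 − 1.96) = Φ(0.854) = 0.804.

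The two-sample t version with 86 degrees of freedom gives 0.795. Both reproduce the stated 0.80. The calculation takes no credit for any covariate.

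**2. Assumed correlations.** The documents give none. Let r1 be the correlation of 28-day PHDD with mean Weeks 3-12 PHDD, r2 that of 7-day PHDD with the same outcome, and r12 the correlation between the two baseline values. Assumed ranges: r1 0.3-0.5, r2 0.4-0.6, r12 0.5-0.7.

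**3. Cut in residual variance from adding the 7-day value to the 28-day value.**

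cut = (r2 − r1·r12)² / [(1 − r12²)(1 − r1²)]

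| r1, r2, r12 | Calculation | Cut |
|---|---|---|
| 0.4, 0.5, 0.6 (midpoint) | 0.26² / (0.64 × 0.84) | 12.6% |
| 0.4, 0.5, 0.5 | 0.30² / (0.75 × 0.84) | 14.3% |
| 0.4, 0.5, 0.7 | 0.22² / (0.51 × 0.84) | 11.3% |
| 0.5, 0.4, 0.7 (smallest) | 0.05² / (0.51 × 0.75) | 0.7% |
| 0.3, 0.6, 0.7 (largest) | 0.39² / (0.51 × 0.91) | 32.8% |

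At the midpoint the residual variance ratio is 0.874, and 1/0.874 = 1.14, equivalent to about 14% more subjects.

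**4. Power.** Take the SD of 1 behind d = 0.60 as the SD left after the covariates already in the model. At the midpoint the effective d is 0.60/√0.874 = 0.642, and power is Φ(0.642 × √22 − 1.96) = Φ(1.05) = 0.853. By partial correlation r (the square root of the cut) of the 7-day value with the outcome:

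| r | Power, normal | Power, t (1 df lost) | n per arm for 80% |
|---|---|---|---|
| none | 0.804 | 0.795 | 44 |
| 0.1 | 0.807 | 0.799 | 44 |
| 0.2 | 0.819 | 0.811 | 42 |
| 0.3 | 0.839 | 0.831 | 40 |
| 0.4 | 0.867 | 0.859 | 37 |
| 0.5 | 0.901 | 0.895 | 33 |

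**5. Chance imbalance.** The between-arm difference in a standardized covariate has SD √(2/44) = 0.213, so a 1.96-SD imbalance is 0.418. Left unadjusted, it moves the estimate by 0.418·r: 0.084 SD at r = 0.2 and 0.209 SD at r = 0.5, or 14% to 35% of d = 0.60.

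**6. Validity.** In simulated trials with 44 per arm and no treatment effect (20,000 per setting, r = 0.2 and 0.4), rejection rates without the extra covariate were 0.049 and 0.051. With it they were 0.048 and 0.052.

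**The case against.** The strongest reply is that SAP 9.4.3 already deals with this. SAP 9.4.1 sends the primary endpoint there, the candidate list is open, each endpoint may have its own covariates, and selection is done blinded. At the assumed r2 of 0.4-0.6, 7-day PHDD would clear the 0.20 threshold. That stands to this extent: a reader might infer that the plan shuts out pre-randomization drinking, and it does not. But the route only permits inclusion, it rests partly on judgment, and the screen as written is not run against the primary endpoint. Naming the secondary endpoints alone may be a drafting slip, but it still needs correcting.

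Second, the 28-day window is inferred. SAP 9.3 and Listing 7 are descriptive, 5.1.8 concerns the WHO endpoint, and Table 14 shows both windows under a baseline title. This is correct, and it is a reason to state the window in 9.4.1.

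Third, the gain rests on assumption. A 7-day value, truncated by the entry rule, need not predict better than a 28-day value. This also stands; the low end of the range is close to no gain.

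Fourth, no minimum screening length is stated. If randomization follows consent by fewer than 7 days, the two windows overlap. Overlap reduces the gain but does no harm to the comparison.

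**Conclusion.** The point holds as a weakness in precision and prespecification. One drinking covariate is fixed, its window is not stated where the model is defined, and a second baseline value that is already collected and tabulated has no assured place in the model.

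A reader might go further and infer that the primary comparison is biased, that type I error is inflated, or that the trial is underpowered. The documents do not support any of these. Randomization protects the comparison, chance imbalance is already reflected in the standard error, and the stated 0.80 power is reached without any covariate gain. Nor does a table row for change before randomization show that such change will be large.

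The size depends on correlations the documents do not give: a cut in residual variance of about 1% to 33% over the assumed range, about 13% at the midpoint, and about 2 points of power or less if the partial correlation is 0.2 or below. The Table 14 defect needs no such assumption, although the documents do not say how many subjects would have no abstinent day. The change should be made because it is cheap and planned power has no margin.

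**What to change.** Before unblinding:

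- In SAP 9.4.1, state that baseline PHDD is measured over the 28 days before screening, and add PHDD in the 7 days before randomization as a second fixed covariate.
- For the continuous weekly drinking secondary endpoints (percentage of days abstinent, drinks per week, drinks per drinking day), add the matching 7-day measure in the same way.
- In SAP 9.4.3, extend the correlation matrices to the primary endpoint.
- In Table 14, replace percent change with the absolute difference between the two windows.

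The cost is a few sentences in the SAP, a change to one table shell and one degree of freedom per model. No new data are needed.
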